3.3.3.3.1 Continue to monitor urine output and pH

3.3.3.3.2 Hydration should be resumed if needed to maintain urine pH  $\geq 7.0$  to  $\leq 8.0$  and urine output  $>100$  mL/hour

3.3.4 High-Dose Methotrexate with sodium bicarbonate followed by leucovorin rescue

3.3.4.1 Prior to HIGH-DOSE METHOTREXATE infusion, administer anti-emetic medication. Recommended: ondansetron 24 mg orally 1 hour prior to methotrexate, followed by ondansetron 8 mg orally every 8 – 12 hours for 3 days.

3.3.4.2 On day 2, after urine pH  $\geq 7.0$  and urine output  $>100$  mL/hour are confirmed, administer methotrexate  $6000$  mg/ $m^2$  IV over 4 hours (goal start time for methotrexate administration is 9AM – 10AM):

3.3.4.2.1 Administer methotrexate  $6000$  mg/ $m^2$  x 1 bottle with  $NaHCO_3$  25-75 mEq diluted in 5% Dextrose/0.45% Sodium Chloride Injection (qs.) 1000 mL at 250 mL/hour (i.e., over 4 hours).

3.3.4.2.2 Order daily serum methotrexate levels timed to start 24 hours after methotrexate administration begins and continue daily measurements until the serum methotrexate level is  $\leq 0.05$  mcMol/L.

3.3.4.2.3 Continue IV or oral hydration with urine alkalinization (pH  $\geq 7.0$  to  $\leq 8.0$ ) until serum methotrexate level is  $\leq 0.05$  mcMol/L (see sections 3.3.3.3 and 3.3.4.2)

3.3.4.3 **Leucovorin rescue**, starting 24 hours after methotrexate administration began (generally on day 3):

3.3.4.3.1 Administer leucovorin calcium  $100$  mg/ $m^2$  per dose IV (preferred) or levoleucovorin calcium  $50$  mg/ $m^2$  per dose IV every 6 hours until the serum methotrexate level is  $<0.5$  mcMol/L.

3.3.4.3.2 When the methotrexate level is  $<0.5$  mcMol/L, parenterally administered leucovorin or levoleucovorin may be replaced with leucovorin administered

orally (10 mg/m^2, or a fixed 25-mg dose for patients with BSA <2.5 m^2), until the methotrexate level is  $\leq 0.05$  mcg/L.

3.3.4.3.3 For patients with delayed methotrexate clearance, see sections 3.4.3 and 3.4.4.

3.3.5 Filgrastim

3.3.5.1 Routine use of filgrastim is not required for this therapy

3.3.5.2 Do not administer filgrastim within 24 hours before administering methotrexate

3.3.5.2.1 If filgrastim has already been administered, delay methotrexate until >24 hours have passed since filgrastim administration

3.3.5.2.2 Do not administer filgrastim after methotrexate administration until methotrexate levels have decreased to  $< 0.05$  mcg/L.

3.3.5.3 Pegfilgrastim may not be used.

3.3.5.4 Indications for filgrastim use for patients on this study:

3.3.5.4.1 HIV-related neutropenia

- Includes neutropenia related to antiretroviral therapy, or other HIV-disease-related therapy

3.3.5.4.2 Methotrexate-related neutropenia

3.3.5.4.3 Rituximab-related neutropenia

- Includes delayed-onset neutropenia

3.3.5.5 Filgrastim doses will be individually titrated according to the clinical scenario.

3.3.5.6 Filgrastim 300-480 mcg/day subcutaneously may be used as needed to maintain an absolute neutrophil count  $\geq 1000$  cells/mm^3. Filgrastim will not be administered more frequently than once daily. Intravenous administration may be utilized.

3.3.6 Highly Active Antiretroviral Therapy (HAART)

3.3.6.1 Whenever possible, patients should be taking HAART as soon as is feasible

3.3.6.2 HAART interruptions for toxicity and tolerance are allowed

3.3.6.3 Refusal to adhere to HAART is not permitted, as it is considered part of the oncology therapy for this protocol

3.3.6.4 A regimen of highly active anti-retroviral therapy will be initiated as soon as feasible in all patients. Treatment will in general be based on Department of Health and Human Services Antiretroviral Guidelines for Adults and Adolescents found at <http://www.aidsinfo.nih.gov/guidelines/>. Particular events may require treatment suspension, modification and will be considered individually for best medical care. Therapy may be managed by NCI and or NIAID co-investigators on this protocol or on the NIAID sister protocol.

3.3.6.5 Order HLA B\*5701 Pharmacogenetic test at baseline to evaluate for possible use of abacavir. Recommend a tenofovir-free regimen to avoid potential nephrotoxicity and potential deleterious effect on methotrexate renal excretion.

### **3.4 TREATMENT MODIFICATIONS: HIGH-DOSE METHOTREXATE WITH LEUCOVORIN RESCUE AND RITUXIMAB**

3.4.1 Rituximab

3.4.1.1 For infusion related events or hypersensitivity reactions, the infusion rate should be slowed (e.g. for moderate flu-like symptoms of fever, chills, rigors; other infusion related reactions such as nausea, urticaria, pruritus, rash, fatigue, headache) or infusion of the drug should be interrupted or discontinued as clinically indicated (e.g. for reactions such as angioedema, hypotension, bronchospasm); following appropriate treatment and/or resolution of the reaction(s), administration of rituximab may be reinitiated at a slower infusion rate (one-half the previous infusion rate), and the rate of infusion may be incrementally increased as tolerated.

3.4.2 High-dose methotrexate

3.4.2.1 The creatinine clearance (CrCl) will be calculated by method of Cockcroft-Gault prior to each cycle (see [Appendix 4](#)). If CrCl is  $\geq 100$  mL/min, then no dose adjustment is necessary. If CrCl is  $< 100$  mL/min, then the methotrexate dose is adjusted by the fraction of CrCl less than 100 mL/min (e.g., methotrexate dose =  $6000 \text{ mg/m}^2 \times \text{CrCl}/100$ ).

3.4.2.1.1 For estimated creatinine clearance  $< 100$  mL/min, a 24-hour urine collection should be obtained *plus* a serum creatinine at the end of the collection period to determine a measured creatinine clearance.

3.4.2.2 Delayed methotrexate serum clearance ( $> 3$  days after methotrexate infusion) may occur and mandates accelerated rescue and continued hydration and alkalinization. The minimum interval between achieving a serum methotrexate level  $\leq 0.05 \text{ mcg/mL}$  and the start of a subsequent treatment cycle is 7 days.

3.4.2.3 For creatinine clearance  $< 60$  mL/min, no methotrexate will be administered. Administer rituximab without methotrexate after discussion with a medically responsible investigator if renal function cannot be expected to be optimized (CrCl  $\geq 60$  mL/min) within 3 days.

3.4.2.4 For transient ALT and/or AST elevations  $\geq 10X$  the upper limit of normal, withhold methotrexate until both ALT and AST are  $\leq 5X$  the upper limit of normal, then permanently reduce methotrexate dosage by 25% for all subsequent cycles beginning with the next cycle.

3.4.2.5 For ANC  $< 1000 \text{ cells/mm}^3$ , delay methotrexate until ANC recovers to  $\geq 1000/\text{mm}^3$ .

3.4.2.6 For platelet counts  $< 50,000/\text{mm}^3$ , delay methotrexate until platelet count recovers to  $\geq 50,000/\text{mm}^3$ .

3.4.2.7 For any other Grade 3 or greater toxicities related to methotrexate, with the exception of hematologic toxicity, hold methotrexate until toxicity abates to Grade  $\leq 2$ .

3.4.2.8 For pulmonary toxicity related to methotrexate, permanently discontinue methotrexate.

3.4.2.9 Note, if toxicity attributed to methotrexate prevents subsequent methotrexate treatment prior to the time of complete response, patient will be considered a treatment failure. Failure of toxicity to resolve and thus creating dose delays in excess of 15 days will result in methotrexate discontinuation.

3.4.3 Leucovorin

- 3.4.3.1 In the case of delayed early methotrexate elimination (see Table 1 below) and/or evidence of acute renal injury, administer leucovorin calcium according to Table 1 until the serum methotrexate level is  $\leq 0.05$   $\mu\text{mol/L}$ .
- 3.4.3.2 If leucovorin is not available (e.g., due to a drug shortage), replace leucovorin with levoleucovorin calcium every 6 hours until serum methotrexate level is  $\leq 0.5$   $\mu\text{mol/L}$ , see Table 1 for dosing.
- 3.4.3.3 Alternatively, glucarpidase (formerly “carboxypeptidase G2”) may be used (see section 3.4.4 below)
- 3.4.3.3.1 Evidence of acute renal injury includes a 100% or greater increase in serum creatinine level at 24 hours after methotrexate administration (e.g., an increase from 0.5 mg/dL to a level  $\geq 1$  mg/dL).

Table 1: Leucovorin and Levoleucovorin dosing for delayed methotrexate clearance

Methotrexate Level	Leucovorin Dose	Levoleucovorin Dose
24 hours: >10 mcmol/L	100 mg/m  IV q 6 hours	50 mg/m  IV q 6 hours
48 hours: >1 mcmol/L	100 mg/m  IV q 3 hours	50 mg/m  IV q 3 hours
60 hours: >2 mcmol/L	200 mg/m  IV q 3 hours	100 mg/m  IV q 3 hours
72 hours: >0.1 mcmol/L	100 mg/m  IV q 6 hours	50 mg/m  IV q 6 hours

**When the methotrexate level is  $\leq 0.5$  mcmol/L, leucovorin/levoleucovorin may be administered as oral leucovorin calcium until serum methotrexate level is  $\leq 0.05$  mcmol/L (see Section 3.3.4.3.2).**

3.4.3.4 In addition to appropriate leucovorin/levoleucovorin therapy, these patients require continuing hydration and urinary alkalinization, and close monitoring of fluid and electrolyte status, until the serum methotrexate level has fallen to  $<0.05$  mcmol/L and renal failure has resolved.

3.4.3.5 Serum methotrexate monitoring levels are now performed at Children's Hospital 7 days per week at 2PM. Specimens collected for methotrexate monitoring must be delivered to the NIH CC Department of Laboratory Medicine's Chemistry Service during morning hours so they can be delivered to Washington's Children's Hospital and processed in a timely manner. This process is designed to obtain same day results for patients on 06-C-0051 so the clinical team can make protocol-defined treatment decisions, such as stopping leucovorin or IV fluids, or implementing treatment for delayed methotrexate clearance with glucarpidase (Voraxaze®)

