3.4.3.5.1 Methotrexate Levels need to be **drawn at scheduled times**

3.4.4 Glucarpidase Rescue of Methotrexate toxicity and Acute Renal Failure

3.4.4.1 Glucarpidase may be utilized in addition to leucovorin or levoleucovorin for methotrexate toxicity in the setting of renal toxicity and delayed methotrexate clearance.

3.4.4.2 Glucarpidase **may ONLY be administered** with the approval of a medically responsible study investigator.

3.4.4.3 Clinical prerequisites:

3.4.4.3.1 Serum methotrexate concentration of  $>10$  mcmol/L at 24-48 hours after methotrexate infusion,

3.4.4.3.2 Urine output decreases (less than 50% excretion of the input hydration) or a serum creatinine  $>1.5$ -times the upper limit of normal, and

3.4.4.4 Documented increase of serum creatinine during the infusion period.

3.4.4.5 Glucarpidase administration:

3.4.4.5.1 Glucarpidase 50 Units/kg of body weight is administered as a single IV injection over 5 minutes.

- 3.4.4.5.2 **Do not administer leucovorin or levoleucovorin within 2 hours either before or after a dose of glucarpidase** because reduced folates such as leucovorin and levoleucovorin are substrates for degradation by glucarpidase.
- 3.4.4.5.3 For the first 48 hours after glucarpidase, administer leucovorin or levoleucovorin at the same dose and schedule as were given prior to administering glucarpidase. At times >48 hours after glucarpidase, administer leucovorin or levoleucovorin based on measured methotrexate concentrations.
- 3.4.4.5.4 Do not discontinue leucovorin or levoleucovorin based on the determination of a single methotrexate concentration <0.05 mcg/L. Leucovorin or levoleucovorin should be continued until the methotrexate concentration has been maintained <0.05 mcg/L for a minimum of 3 days.
- 3.4.4.5.5 Continue hydration and alkalinization of urine as indicated per protocol, or as directed by a medically responsible study investigator.

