**Day 3-End Leucovorin Rescue:**

1. Start leucovorin 100 mg/m^2 IV q6 hours starting 24 hours **AFTER INITIATION** of methotrexate administration.
2. Serum methotrexate monitoring levels is now performed at Children's Hospital 7 days a week at 2 p.m. Specimens collected for methotrexate monitoring must be delivered to the NIH CC Department of Laboratory Medicine's Chemistry Service in the morning so they can be delivered to Washington's Children's Hospital and processed in a timely manner. This process is designed to obtain same day results for patients on 06-C-0051 so the clinical team can make protocol defined treatment decisions, such as stopping leucovorin or IV fluids, or implementing treatment of delayed methotrexate clearance with glucarpidase (Voraxaze®).
3. 24 hours **AFTER INITIATION** of methotrexate, draw red top tube for serum methotrexate level. Methotrexate Levels need to be **drawn at scheduled time**.
4. Repeat every 24 hours: 48 hr, 72 hr, 96 hr, until methotrexate monitoring no longer required.
5. Check methotrexate levels same day, evaluate for delayed methotrexate clearance. Notify Research team for:
  - a. Methotrexate > 10 mcg/L at 24 hours
  - b. Methotrexate > 1 mcg/L at 48 hours
  - c. Methotrexate > 0.1 mcg /L at 72/hours
  - d. For **delayed methotrexate** elimination see pages 26 and 27 3.4.3), Table 1 (Leucovorin dose at 24, 48, 60 and 72 hours), and 3.4.4 for use of glucarpidase guidelines.
6. Stop **intravenous** leucovorin and switch to oral leucovorin 25 mg PO (Alternative 10 mg/m^2 PO) q6 hours
  - a. If methotrexate level is <0.5 mcg/L, see section 3.3.4.3.2
  - b. Patient does **NOT** have delayed methotrexate clearance (Defined, Point 5 above.)
  - c. Discuss discontinuing IVF research team

7. Stop **oral** leucovorin and urine monitoring once serum methotrexate level is  $\leq$  0.05 mcmol/L

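### Read by its time label, Table 1's uncapped 72-hour row halves leucovorin rescue for a patient put on every-3-hour dosing at 48 hours, even if methotrexate is still above 1 mcmol/L

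*Combined protocol and SAP*

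**What the plan says.** All references are to the combined protocol and SAP.

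- **Routine rescue (3.3.4.3.1).** Leucovorin 100 mg/m2 "per dose IV every 6 hours until the serum methotrexate level is" below 0.5 mcmol/L. Below that level, section 3.3.4.3.2 allows an oral dose.
- **Delayed clearance (3.4.2.2).** Clearance delayed more than 3 days after the infusion "may occur and mandates accelerated rescue and continued hydration and alkalinization".
- **Which table to use (3.4.3.1).** In delayed early elimination or acute renal injury, "administer leucovorin calcium according to Table 1 until the serum methotrexate level is" 0.05 mcmol/L or below.
- **Table 1.** There are four rows, each keyed to a time and a level: 24 h (above 10 mcmol/L), 48 h (above 1), 60 h (above 2) and 72 h (above 0.1). Each gives a lower cut-off only.
- **Levoleucovorin (3.4.3.2).** If leucovorin is unavailable, "replace leucovorin with levoleucovorin calcium every 6 hours until serum methotrexate level is" 0.5 mcmol/L or below. The same sentence refers to Table 1 for dosing.
- **Note under Table 1.** At 0.5 mcmol/L or below, "leucovorin/levoleucovorin may be administered as oral leucovorin calcium until serum methotrexate level is" 0.05 mcmol/L or below.
- **Appendix 9, Day 3 to end of rescue.** Levels are drawn daily (item 4: "Repeat every 24 hours: 48 hr, 72 hr, 96 hr, until methotrexate monitoring no longer required"). The research team is notified at the 24-, 48- and 72-hour cut-offs (item 5). Item 5d sends delayed cases to "Table 1 (Leucovorin dose at 24, 48, 60 and 72 hours), and 3.4.4 for use of glucarpidase guidelines". Item 6b allows the oral switch only when clearance is not delayed.

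**The concern.** Table 1 sets rescue after 6,000 mg/m2 of methotrexate in the patients who clear it slowly. A patient above 1 mcmol/L at 48 hours goes onto every-3-hour dosing. At the 72-hour draw the same patient, if still above 0.1 mcmol/L, falls within the 72-hour row, which is every 6 hours however high the level is. Applied as labelled, that row reduces rescue in a patient whose methotrexate may not have fallen at all, at the point where section 3.4.2.2 asks for acceleration.

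Section 3.4.3 gives an end point for Table 1 dosing but no rule for moving between rows. The protocol does write such a rule elsewhere. For the first 48 hours after glucarpidase, section 3.4.4.5.3 says to "administer leucovorin or levoleucovorin at the same dose and schedule as were given prior to administering glucarpidase", and only then to dose by measured level. Table 1 has no equivalent sentence.

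What is at stake is the adequacy of a safety rescue dose, not the trial's inference.

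**Working it through.** The protocol states no daily totals, so there is no stated figure to reproduce. The check converts each instruction to a daily dose and compares them.

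**Formula.** Daily dose = single dose × 24 / interval in hours (every 6 h = 4 doses, every 3 h = 8 doses).

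| Source | Level (mcmol/L) | Leucovorin | Daily dose (mg/m2) |
|---|---|---|---|
| Routine, 3.3.4.3.1 | until below 0.5 | 100 mg/m2 every 6 h | 4 × 100 = 400 |
| Table 1, 24 h | above 10 | 100 mg/m2 every 6 h | 4 × 100 = 400 |
| Table 1, 48 h | above 1 | 100 mg/m2 every 3 h | 8 × 100 = 800 |
| Table 1, 60 h | above 2 | 200 mg/m2 every 3 h | 8 × 200 = 1,600 |
| Table 1, 72 h | above 0.1 | 100 mg/m2 every 6 h | 4 × 100 = 400 |

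**Step-down.** Take an illustrative patient at 1.5 mcmol/L at both 48 and 72 hours. The 48-hour row gives 800 mg/m2/day and the 72-hour row gives 400. The ratio is 800 / 400 = 2, with no change in level.

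**In milligrams.** Body surface area is not given, so it is assumed, with a range:

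- 1.5 m2: 1,200 against 600 mg/day, a gap of 600.
- 1.8 m2: 1,440 against 720 mg/day, a gap of 720.
- 2.2 m2: 1,760 against 880 mg/day, a gap of 880.

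**Against routine rescue.** At 0.5 mcmol/L or above, the 72-hour row and routine rescue are the same: 400 / 400 = 1.0. Between 0.1 and 0.5 mcmol/L the 72-hour row is stronger than the routine option, which may be oral at 10 mg/m2 every 6 h (4 × 10 = 40 mg/m2/day).

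**Levoleucovorin.** Table 1 gives 50 mg/m2 every 3 h at 48 hours: 8 × 50 = 400 mg/m2/day. The 6-hour interval in section 3.4.3.2 gives 4 × 50 = 200. At 1.8 m2 that is 720 against 360 mg/day, again twofold.

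**Timing.** Table 1 levels are timed from the start of a 4-hour infusion, so the 72-hour draw falls 72 − 4 = 68 hours after the infusion ends. Three days after its end is 72 + 4 = 76 hours on the Table 1 clock. The 72-hour row is the last row, so it is still the applicable one when the 3-day trigger in section 3.4.2.2 is reached.

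**Not counted.** The 60-hour dose needs a draw that is not on the 24-hourly schedule in Appendix 9, so the size above rests on the 48-hour row alone.

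**The case against.** **The rows may not be ambiguous.** Each row carries a time, so a 72-hour level points to the 72-hour row. This stands, and it makes the step-down the natural result of following the table. The other reading, that section 3.4.3.1 carries the 48-hour dose forward until 0.05 mcmol/L, is possible but is not written.

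**Acceleration is undefined.** Section 3.4.2.2 does not say that accelerated means more mg/m2 than routine. That is fair, and it softens the conflict. It is still hard to call a halved dose equal to routine rescue accelerated.

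**Safeguards exist.** Care is in-patient at one centre, levels come back the same day, the research team is notified at each cut-off, and hydration and alkalinization continue. These limit the risk, and investigator judgement may well settle an individual case. But item 5d of Appendix 9 returns the team to the same table. Glucarpidase is not a general backstop, because section 3.4.4.3 requires a level above 10 mcmol/L at 24 to 48 hours plus renal criteria. A patient at 8 mcmol/L at 24 hours and 3 at 48 hours would be on every-3-hour rescue without meeting that level criterion.

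**The oral texts.** A reader might infer that the note under Table 1 contradicts item 6b of Appendix 9, since item 5c counts a level above 0.1 at 72 hours as delayed (its unit is garbled in this copy and is taken as mcmol/L). The documents do not support so firm a reading. The note is permissive, IV dosing satisfies both texts, and sections 3.3.4.3.3 and item 5d send delayed patients to section 3.4.3, so item 6b may limit only the routine switch. What remains is that no text says which governs.

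**Levoleucovorin.** The substitution applies only in a shortage and defers to Table 1. The point is minor, but the stated interval does differ from the rows it cites.

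**Conclusion.** The concern holds for a defined group: patients put on every-3-hour dosing at 48 hours whose level is still above 1 mcmol/L at 72 hours. For them, Table 1 read by its time labels halves leucovorin from 800 to 400 mg/m2/day, which is the routine dose. At an assumed 1.8 m2 that is 720 mg/day less (600 to 880 mg over 1.5 to 2.2 m2). Section 3.4.3.2 adds a smaller internal conflict on the levoleucovorin interval.

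A reader might infer that the 72-hour row under-rescues everyone with delayed clearance, or that patients are known to be harmed. The documents support neither. Between 0.1 and 0.5 mcmol/L the row exceeds the routine option, and nothing in the documents quantifies harm or the number of patients affected.

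The twofold figure is arithmetic on the stated doses. It assumes only that the 72-hour row replaces the earlier one, as its label suggests. The primary endpoint, sample size and analysis are unaffected. This should be fixed because the text concerns a safety rescue and the correction is small.

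**What to change.** **(a) Main change.** Add one line under Table 1, for both drug columns: *A patient already on a 48- or 60-hour dose is not reduced by the 72-hour row while the level remains above 1 mcmol/L; the 72-hour row is a minimum dose.* The 1 mcmol/L threshold is carried over from the 48-hour cut-off. The documents do not justify it at 72 hours, so the investigators should confirm it. In section 3.4.3.2, replace the 6-hour interval with a reference to the Table 1 interval, so that it does not undo this line.

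**(b) Secondary clarification.** State whether the note under Table 1 or item 6b of Appendix 9 governs the oral switch in delayed clearance. The cautious choice is to stay on IV dosing, as in item 6b.

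**Limit of the fix.** At 1 mcmol/L or below, the 72-hour row may still apply to a known slow clearer. From 0.5 to 1 mcmol/L it equals routine rescue. The line sets a floor there and leaves any higher dose to clinical judgement.

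**Cost.** A short amendment, with no added visits or tests. A patient kept on the 48-hour dose receives 800 − 400 = 400 mg/m2/day more leucovorin (about 720 mg/day at 1.8 m2) while the level stays above 1 mcmol/L. If (b) is settled in favour of IV dosing, some patients stay on IV leucovorin longer.

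### For delayed methotrexate clearance, section 3.4.3.2 states a levoleucovorin interval that Table 1 contradicts at 48 and 60 hours, and Table 1's top rescue step depends on a 60-hour level that is not on the draw schedule

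*Combined protocol and SAP*

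**What the plan says.** All methotrexate levels below are read as mcmol/L.

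- **Routine rescue (3.3.4.3.1).** Leucovorin 100 mg/m2 or levoleucovorin 50 mg/m2 is given "per dose IV every 6 hours until the serum methotrexate level is" below 0.5.
- **Delayed clearance, leucovorin (3.4.3.1).** The instruction is to "administer leucovorin calcium according to Table 1 until the serum methotrexate level is" at most 0.05.
- **Delayed clearance, leucovorin unavailable (3.4.3.2).** The instruction is to "replace leucovorin with levoleucovorin calcium every 6 hours until serum methotrexate level is" at most 0.5. The same sentence refers to Table 1 for dosing.
- **Table 1.** The 48-hour row (above 1) gives levoleucovorin as "50 mg/m 2 IV q 3 hours". The 60-hour row (above 2) gives leucovorin as "200 mg/m 2 IV q 3 hours", or levoleucovorin 100 mg/m2 every 3 hours. The last row, "72 hours: >0.1 mcmol/L", returns to leucovorin 100 mg/m2 or levoleucovorin 50 mg/m2 every 6 hours.
- **Draw schedule.** Section 3.3.4.2.2 says "Order daily serum methotrexate levels timed to start 24 hours after methotrexate administration begins and continue daily measurements" until the level is at most 0.05. Appendix 9 (Day 3 to end of rescue, item 4) lists 48, 72 and 96 hours after the 24-hour draw.
- **Assay (3.4.3.5).** Specimens are delivered in the morning for one run a day at 2 PM.
- **Alerts (Appendix 9, item 5).** The research team is notified of levels above 10 at 24 hours, above 1 at 48 hours and above 0.1 at 72 hours. Item 5d then refers the team to Table 1, naming its 60-hour dose.

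**The concern.** Two instructions in one sentence disagree. The text of 3.4.3.2 fixes an interval, and the table it cites doubles the frequency in two rows. A reader who takes the milligrams from the table and the interval from the text loses the 48-hour escalation.

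The second problem does not depend on a shortage. The strongest rescue dose is triggered by a level that no section schedules, and the described logistics give no same-day result for it. The next scheduled row has one low trigger, no upper band, and the routine dose. It does not say whether a dose escalated at 48 hours continues. That fits poorly with 3.4.2.2, which requires accelerated rescue once clearance is delayed beyond 3 days.

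At stake is rescue after 6000 mg/m2 of methotrexate, in the patients who clear it most slowly.

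**Working it through.** **1. Levoleucovorin per day.** Formula: dose per administration × (24 ÷ interval in hours). Doses come from Table 1; the 6-hour interval comes from 3.4.3.2.

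| Table 1 row | Table 1 interval | Table 1, mg/m2/day | At every 6 h, mg/m2/day | Ratio |
|---|---|---|---|---|
| 24 h, >10 | 6 h | 50 × 4 = 200 | 50 × 4 = 200 | 1.0 |
| 48 h, >1 | 3 h | 50 × 8 = 400 | 50 × 4 = 200 | 0.5 |
| 60 h, >2 | 3 h | 100 × 8 = 800 | 100 × 4 = 400 | 0.5 |
| 72 h, >0.1 | 6 h | 50 × 4 = 200 | 50 × 4 = 200 | 1.0 |

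Text and table agree at 24 and 72 hours and conflict at 48 and 60 hours. The routine levoleucovorin dose is also 50 × 4 = 200 mg/m2/day, so the text's interval at 48 hours gives routine rescue.

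**2. Which rows the schedule reaches.** Scheduled draws are multiples of 24 hours: 24, 48, 72, 96. Sixty is not among them.

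Section 3.3.4.2 states that the "goal start time for methotrexate administration is" 9 to 10 AM, on Day 2. From a 9 AM start (10 AM in brackets):

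- 48-hour sample: Day 4, 9 AM (10 AM). The 2 PM run falls at 53 h (52 h).
- 60 hours: Day 4, 9 PM (10 PM). The next run is Day 5, 2 PM, at 77 h (76 h), which is 17 h (16 h) after the draw.
- 72-hour sample: Day 5, 9 AM (10 AM). It joins the same run, at 77 h (76 h).

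On the described logistics, a 60-hour sample would therefore be reported no sooner than the 72-hour sample.

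**3. Size of the reachable conflict.** From the 48-hour result to the 72-hour result is 77 − 53 = 24 h (76 − 52 = 24 h). Shortfall: 8 × 50 − 4 × 50 = **200 mg/m2** of levoleucovorin.

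**4. Leucovorin steps per day.** Routine: 100 × 4 = 400 mg/m2. 48-hour row: 100 × 8 = 800. 60-hour row: 200 × 8 = 1600. 72-hour row: 100 × 4 = 400, the same as routine. Nothing in Table 1 says whether the 72-hour row replaces the 48-hour dose. Section 3.4.3.1 can be read as continuing it.

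**The case against.** **The table governs.** Section 3.4.3.2 gives no milligram dose, so the reader must go to a Table 1 cell that prints its own interval. Someone who uses the whole cell is not misled, and the branch applies only when leucovorin is unavailable. This stands, and it limits the first part to a conditional risk. It does not remove the contradiction.

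**The 60-hour dose is halved too.** A reader might infer this from 400 against 800 mg/m2/day. On the scheduled draws that row is not reached, so no dose there is halved.

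**A 60-hour level is ruled out.** The documents do not say so. Section 3.8.3.6.1 requires draws at their set times but does not forbid extra ones, and the morning start is only a goal. If levels only fall (an assumption), every patient above 2 at 60 hours was already above 1 at 48 hours. That patient has been flagged and, under Table 1, is on leucovorin 800 mg/m2/day. The team could order another level. This stands as a safeguard, but no such draw or assay is described.

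**A patient above 2 at 72 hours gets a quarter of the intended dose.** The ratio 400 ÷ 1600 = 0.25 is tempting. It needs the least sensible reading, in which the 72-hour row cancels the earlier escalation despite the accelerated-rescue rule in 3.4.2.2. Continuing the 48-hour dose gives 800 ÷ 1600 = 0.5. A team could also treat a level above 2 at 72 hours under the 60-hour row, at the full 1600. The documents do not choose among these, so the finding is ambiguity and not a quarter dose.

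**Glucarpidase covers these patients.** Only in part: 3.4.4.3 requires a level above 10 at 24 to 48 hours plus renal signs. A patient above 2 who was never above 10 in that window is not covered.

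**Frequency is unknown.** This stands. The documents give no rate of delayed clearance, and methotrexate is withheld below a creatinine clearance of 60 mL/min and scaled down below 100 (3.4.2).

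**Conclusion.** The concern holds in limited form and should be corrected as a patient-safety matter. There are three defects:

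1. Section 3.4.3.2 contradicts Table 1 at 48 and 60 hours. On the scheduled draws the discrepancy is 200 against 400 mg/m2/day in the 48-hour row, or 200 mg/m2 over 24 hours. It requires both a leucovorin shortage and a reader who takes the interval from the text. The 24-hour span assumes a constant delay from the 2 PM run to the result.
2. Table 1's top step has no scheduled level to trigger it.
3. The 72-hour row does not say whether an earlier escalation continues.

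How many patients would be affected cannot be estimated from the documents.

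A reader might infer that the primary endpoint is compromised, since 3.4.2.9 counts methotrexate toxicity that stops treatment before complete response as failure. The documents do not support that step. They give no link from these rescue doses to a number of failures, and the sample size, test and analysis are untouched.

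**What to change.** **(a) Section 3.4.3.2.** Replace the stated interval with: levoleucovorin at the dose and interval in Table 1, IV until the level is ≤0.5 mcmol/L, with rescue continued until ≤0.05 mcmol/L.

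**(b) Table 1.** Keep the 60-hour row at its existing doses and relabel its trigger: 60 hours or the first available level thereafter (including the scheduled 72-hour level), >2 mcmol/L. Add that a dose escalated at 48 hours is not reduced to the 72-hour row while the level remains >1 mcmol/L. Keeping the row preserves the earlier escalation where a team does obtain a 60-hour level; deleting it would lose that.

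**(c) Alignment.** Clinicians and pharmacy confirm the values. Appendix 9 item 5 and the order set are brought into line.

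**Cost.** A short amendment, an order-set update and some additional leucovorin or levoleucovorin doses. No draws or visits are added. Patients affected by (b) are above 1 mcmol/L and so still on IV rescue and IV hydration, which may be relaxed only below about 0.5 (3.3.3.3, 3.3.4.3.2). Extra inpatient days are therefore not expected.

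**Limit.** Without an extra draw, a patient above 2 at 60 hours who has fallen to 2 or less by 72 hours still does not reach the top step. If still above 1, that patient keeps the 48-hour dose.
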